Work-place evaluation is an important aspect of the study. Each participant will be asked to provide contact information for a direct supervisor who is familiar with on-site work performance. Questions focus on reliability, efficiency of task completion, quality of work performance, independence on the job, as well as military readiness. SMs functioning at their duty station will be assessed by the Checklist of Military Activities of Daily Living (M-ADL). The M-ADL includes 15 items that are detailed in Table 4. In addition to the standard items, 3 items assessing cognitive performance at the workplace will be included. Each item is rated on a Likert scale from "0: Unable to Participate (medical/administrative waiver)" to "7: Complete Independence (timely, safely)". Total score will be used as the primary variable of interest.

If participants are okay with supervisors being contacted the supervisors will fill out a blank survey and return it to the researchers. Participants will not see their supervisor's responses, and supervisors will not see any of the participant's study data. Surveys will be administered online via a secure email link:

https://nhcpr.gov1.qualtrics.com/jfe/form/SV_71npwM0iv2K9XOm

Because work performance evaluation may be a sensitive topic for this population, participants will be asked during the consent process if they give permission for the study team to contact their direct supervisor. If participants do not want their supervisor contacted, then the M-ADL will not be administered. We do not anticipate that the use of the M-ADL will have a direct negative impact on the subject; however, by participating in the M-ADL portion of the study, participants risk that their supervisors will know about the study, and therefore, their participation is no longer anonymous. If participants do not want to accept this risk, they can opt out of this portion of the study.

Study Intervention

Participants will attend two in-clinic sessions per week with a licensed Physical Therapist or Exercise Physiologist and complete three sessions per week independently outside of the clinic. Each session will be 1 hour in duration, 5 days a week for 8 weeks, for a total of 40 hours. Both SAET and SCG interventions will be completed by a trained licensed Physical Therapist or Exercise Physiologist.

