During the initial therapy session, participants will perform the Buffalo Concussion Treadmill Test (BCTT) to see if they are exercise intolerant or not based on symptom exacerbation (Chizuk, Willer, Horn, Haider, & Leddy, 2021; Haider, Johnson, et al., 2019; Haider, Leddy, et al., 2019). Participants randomized to the SAET intervention will complete a combination of aerobic and resistance training exercises for a total of 40 hours. A sample of the sessions, concepts, activities, and time-per phase are detailed in **Figure 2**. SAET will be prescribed and adapted to the participant's personal needs (e.g., adjustments for orthopedic injury) based on evaluations by an Exercise Physiologist and Physical Therapist. Exercise will be adjusted to maintain sub-symptomatic levels, meaning that if a patient's neurobehavioral symptoms increase with activity, the intensity and/or exercise will be modified. Furthermore, participants will be asked to fill out an Exercise Habits Questionnaire (EHQ) in order to capture the exercises they are currently doing and the exercise equipment available to them in order to best prescribe a personalized treatment. Participants will be monitored for safety and receive feedback from the trainer on the execution of the activity regimen during in-clinic sessions.

Each workout will be structured in a similar format. The first 5 minutes will be devoted to stretching and warm up exercises. Then the next 20 minute segment will be devoted to light to moderate aerobic exercise in order for participants to meet their predetermined heart rate threshold (HR_t), or 90% of their max HR, from the BCTT. The aerobic exercise can be completed in any format preferred by the participant with recommendations for treadmill, row machine or stationary bicycle. HR will be measured by an exercise wearable device which gives in the moment feedback. In exercises completed at home, the first 20 minutes will also be aerobic exercise with HR goals as the target variable with open format in terms of the type of aerobic exercise (walk, jog, bicycle, or equipment). When exercising at home, the participant will be asked to wear the exercise

wearable device and complete an Exercise Compliance Questionnaire (ECQ) logging the time of exercise and type of exercise via Qualtrics survey tool.

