Exercise Habits Questionnaire: To best prescribe a personalized exercise treatment, participants will be asked to complete an exercise habits questionnaire to capture their current exercise routine and available exercise equipment to them.

Figure 1. Study Procedure Overview

[figure not shown]

Figure 2. Example of SAET Program

Your clinician has given you a prescription for light to moderate aerobic and resistance training exercise. Each week, you will be given a specific workout to complete for 5 days. Two of these days will be completed with a trainer in the clinic and three other days will be completed on your own time.

This means you will exercise each day, but you will keep your heart rate at a specific level that is lower than it would get to during regular exercise. Your doctor has decided on a heart rate that is safe for you based on the results of your exercise test.

You can perform aerobic exercise how you want (i.e. walking, jogging, stationary cycling), but it is important to avoid a lot of neck motion during exercise. Exercise should include: A short warm-up such as stretching or walking (5 minutes), a minimum of 20 minutes at the prescribed heart rate, a minimum of 20 minutes on resistance exercises provided by your trainer, and a cool-down such as stretching or walking (5 minutes).

It is very important that you only exercise according to your prescription, and that you follow the instructions given by your doctor very carefully. Even if you start to feel better while you are at home, you should not change the heart rate at which you are exercising until you have seen your doctor again. Each clinical visit, your doctor will see how you are doing and provide a new exercise prescription if you have not recovered.

For this exercise prescription, you should use the wearable device provided to you at study enrollment. Whenever you are exercising, you will wear the monitor to help you track your heart rate.

Here is your exercise prescription that you should follow until your next follow-up visit:

Your treadmill test was performed on

± 5

We would like you to exercise at a heart rate of **bpm**

When to stop?

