If you experience an increase in your current symptoms (by 2 points on a 0-10 scale) or onset of two new symptoms of concussion while exercising at home and cannot continue, please stop for that day and try again the following day. If you experience a prolonged or severe increase of your concussion-related symptoms during exercise, then do not perform the prescribed exercises and contact your doctor.

Example Day 1 Prescribed Exercise Program

REMINDER: Note your target heart rate (page 1), wear your heart rate monitoring device, and stop exercising if your symptoms worsen.

Day 1: With Trainer

- 1: 5 Minutes Warm Up
- 2: Minimum 20 minutes at target heart rate
- 3: Minimum 20 minutes resistance training (see below)
4. 5 Minute Cool Down

Resistance Work-Out and Medications Day 1

Exercise 1: Sit Ups: 20 standard sit-ups, 3-5 sets

Modifications: 30 second plank or 20 crunches

Exercise 2: Standard Bench Press, 3-5 sets with 10 repetitions

Modifications: dumbbell chest press or push ups

Exercise 3: Dumbbell Shoulder Press, 3-5 sets with 10-12 repetitions

[figure not shown]
Modifications: Banded shoulder press or machine shoulder press

Exercise 4: Incline Dumbbell Fly, 3-5 sets with 10-12 repetitions

Modifications: incline chest press or decline push up

Exercise 5: Triceps Pushdown, 3-5 sets with 10-12 repetitions

Modifications: Triceps Dip, Bent Over Triceps Extension

Figure 3. Example SCG Program

YOUR PERSONAL STRETCHING PRESCRIPTION

Your doctor has given you a prescription for light stretching. For this research study, it is important that you follow the instructions given by your doctor below very carefully!

You will do stretching exercises each day, without doing any other type of exercise that gets your heart rate up. Your doctor has decided on a stretching routine that is safe for you, and that should not cause you to

have any concussion symptoms. If your doctor appointment is during Days 1-6 of a stretching cycle, do not do the stretches for that day. The day after your appointment, resume doing stretches.

You will be asked to tell us how you are feeling and your activity level.

Please wear your heart rate monitoring device during the exercise.

HERE IS THE PRESCRIPTION THAT YOU MUST FOLLOW

Please see the attached sheet for instructions/demonstrations of stretches that you should do each day/week. They change each day, so be sure to follow the booklet as written.

[figure not shown]
Example Day 1 Prescribed Stretching Program

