14.2 Measures to Minimize Risk of Harm (Precautions, safeguards)

For each research procedure or intervention, describe all measures to minimize and/or eliminate risk of harms to subjects and study personnel

Participants will be instructed to stop exercising for that day if they experience an increase in current symptoms (by 2 points on a 0-10 scale) or onset of two new symptoms of concussion while exercising at home. Also, if participants experience a prolonged or severe increase of concussion-related symptoms during exercise, they should not perform the prescribed exercises and contact their doctor.

Additionally, steps will be taken to ensure participant comfort. Study evaluations will be conducted in comfortable, quiet, and clean testing rooms at the Intrepid Spirit Center. Study personnel will be sensitive to patient discomfort and offer breaks and encouragement when needed and when appropriate.

If participants do not wish for their supervisors to be contacted regarding their job performance through the administration of the M-ADL, participants may opt out of this portion of the research.

If subjects require emergency care for any reason related to the study the NHCP is accessible on base. Adverse events will be reported to the Principal Investigator and IRB within 5 days, as per governing regulations.

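### The home stop rule on the SAET participant sheet adds a condition, *and cannot continue*, that the same rule in section 14.2 does not have

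*Protocol*

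**What the plan says.** The rule for stopping a home exercise session appears in two places in the protocol.

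- **Section 14.2** (measures to minimise risk) says which instruction participants will receive. Its first trigger is worded "stop exercising for that day if they experience an increase in current symptoms (by 2 points on a 0-10 scale"). Its second trigger is worded "onset of two new symptoms of concussion while exercising at home. Also, if participants experience a prolonged or severe increase". The first sentence of that last quote ends after the home setting. The next sentence begins a separate rule for prolonged or severe increases.
- **Section 10.1, Figure 2, *When to stop?*** is the text addressed to the SAET participant. It opens "If you experience an increase in your current symptoms (by 2 points on a 0-10 scale") and continues with the second trigger: "onset of two new symptoms of concussion while exercising at home and cannot continue, please stop for that day". The participant is to try again the next day.

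Both places then give the same second tier in substance: with a prolonged or severe increase, do not do the exercises and contact the doctor.

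Section 10.1 also says that participants "complete three sessions per week independently outside of the clinic", in addition to two supervised clinic sessions.

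**The concern.** The two texts are close enough in wording that they are plainly meant as one rule. Section 14.2 describes an instruction that participants will receive. Figure 2 is the only participant-facing wording of that instruction in the protocol, and it carries an extra condition. As worded, the sheet is weaker than the safeguard promised in section 14.2.

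What is at stake is participant safety in sessions where no trainer can make the decision. A participant who reaches the symptom threshold but feels able to go on has two different answers in the same protocol.

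**Working it through.** No figure in the plan depends on this point, so there is nothing to reproduce. The check sets the two rules side by side.

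**Terms**

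- A: current symptoms rise by 2 points on the 0-10 scale.
- B: two new concussion symptoms appear.
- C: the participant cannot continue.

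**Rules for a home session**

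- Section 14.2: stop if A or B.
- Sheet, reading 1 (condition attached to both triggers): stop if (A or B) and C.
- Sheet, reading 2 (condition attached to the second trigger only): stop if A, or if B and C.

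The grammar of the sheet's sentence allows either reading.

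**Participant who meets a trigger but can continue (C false)**

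| Trigger met | Section 14.2 | Sheet, reading 1 | Sheet, reading 2 |
|---|---|---|---|
| A only | stop | may continue | stop |
| B only | stop | may continue | may continue |
| A and B | stop | may continue | stop |

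Under reading 1 the sheet departs from section 14.2 in every row. Under reading 2 it departs only where two new symptoms appear without a 2-point rise. Neither reading makes the texts agree. When C is true, the rules give the same answer.

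The table shows only that the rules conflict. Its rows carry no frequencies, so it does not measure impact.

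**Does other text reconcile the two?**

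- The second tier covers prolonged or severe increases. It does not settle what to do at the 2-point or two-symptom threshold.
- The treadmill test in section 10.1 ends at a rise of three or more points on a 1-10 scale. That criterion ends a test and is not a rule for training sessions, so it neither conflicts with nor resolves the home rule.

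**The case against.** The strongest reply is that Figure 2 is labelled an example, while section 14.2 holds the operative commitment and states it correctly. Participants are also seen in clinic twice a week, the rule for severe symptoms is the same in both places, and section 16.1 expects symptoms to be mild and short-lived. All of that limits the weight of the point. It does not remove it. The parts of Figure 2 that vary by person or day are the heart rate, the test date and the Day 1 exercises. The *When to stop?* text is general, and the protocol shows no other participant-facing version of it.

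A reader might infer more than the document supports:

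- **That there are three conflicting stop rules.** The Day 1 page also says "wear your heart rate monitoring device, and stop exercising if your symptoms worsen". This is a one-line reminder on a page marked as a with-trainer day, placed after the full rule, and it reads naturally as shorthand. The other two texts concern exercise at home. It is not a third home rule.
- **That the sub-symptomatic principle settles the matter.** Section 10.1 says that if "neurobehavioral symptoms increase with activity, the intensity and/or exercise will be modified". That speaks of adjusting the exercise, not of stopping for the day, so it does not decide between the two stop rules.
- **That the sheet tells participants to obey its own stop text to the letter.** What it says is "It is very important that you only exercise according to your prescription, and that you follow the instructions given by your doctor very carefully". This refers to the prescription and the doctor's instructions, and the sentence after it concerns the target heart rate. It cannot carry that inference.
- **That most sessions are affected.** Three of five weekly sessions are independent, but that is where the rule applies. It is not a count of sessions in which the two wordings would lead to different conduct.

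**Conclusion.** The discrepancy is real but small. One sentence of the participant sheet adds a condition to a safeguard that section 14.2 states without it, and no reading of that sentence brings the two into line. The conclusion rests on the wording alone, and on taking Figure 2's general text as representative of what SAET participants receive.

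Its practical size cannot be given, because the protocol states no rate for either trigger and no share of participants who would carry on after one. Nothing here shows that a participant would be harmed. No statistical figure changes. The point ranks as a minor correction to safety wording.

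**What to change.** Delete *and cannot continue* from the *When to stop?* text in Figure 2. The sentence then goes straight from the two triggers to stopping for that day and trying again the next, as in section 14.2. Make the same deletion in any issued copy of the sheet that carries those words.

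Leave the Day 1 reminder unchanged. Pointing it to the home rule would loosen a stricter prompt and would send a supervised session to a rule written for exercise at home.

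The cost is three words in one participant document. Sample size, visits, treatment content, endpoints and analysis stay as they are.

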10.2 Data Collection

Describe all the data variables, information to be collected, the source of the data, and how the data will be operationally measured.

All surveys, questionnaires, and other instruments will be aligned with Federal Interagency Traumatic Brain Injury Research Informatics System (FITBIR) when possible. FITBIR is a central repository for data from TBI studies built by the National Institutes of Health and the Department of Defense. Key FITBIR common data elements (CDE) include: age, gender,

education, marital status, military branch, rank, military occupational specialty (MOS), Combat Exposure Scale (CES), Neurobehavioral Symptom Inventory (NSI), injury date and time based on administration of the OSU-TBI ID. The legal name at birth, and city and country of birth are being collected to create the Global Unique Identifier (GUID) as required for submission of CDE to FITBIR.

The GUID Tool is a customized software application created by FITBIR that generates a Global Unique Identifier for each study participant. The GUID is a subject ID that allows researchers to share data specific to a study participant without exposing personally identifiable information (PII). The GUID is created locally and made up of random alpha-numeric characters and is NOT generated from PII/PHI. As such, it has been approved by the NIH Office of General Counsel. GUID Generation complies with HIPAA regulations for the protection of PII/PHI.

The following PII is required to generate a GUID: complete legal given (first) name, complete legal additional name, complete legal family (last) name, day of birth, month of birth, year of birth, name of city/municipality in which subject was born, and country of birth. Identifiers collected will be kept separate from study data. Identifiers will be kept in a secure password protected spreadsheet on the hospital server and will serve only for study staff to correctly identify research participants and create study IDs. Study data will be coded with a study IDs.

The study is a randomized clinical trial among active duty service members with persistent cognitive complaints following mTBI, comparing a prescribed sub-symptomatic adaptable exercise treatment (SAET) to an active stretching control group (SCG). SAET overall effectiveness will be assessed by symptom resolution. Additional exploratory aims will include cognitive performance, physiological adaptation and locomotion as well as functional changes in military performance. These items will be addressed in the following aims:

Neurobehavioral Symptoms (Primary Aim) will be assessed using the Neurobehavioral Symptom Inventory (NSI) which captures multiple neurobehavioral symptoms including cognitive, somatosensory, vestibular and affective.

Sub-aim 1 Cognitive Status: To determine if SAET is effective at improving cognitive impairment among SMs with persistent complaints from MTBI.

Sub-Hypothesis 1: There will be a greater decrease in the Global Deficit Scores (GDS; an overall measure of cognitive impairment) post-SAET in comparison to the control condition.

Sub-aim 2 Physiological Adaptation: To measure physiological adaptation associated with SAET compared to the control condition.

Sub-Hypothesis 2: SAET will be associated with improved cerebrovascular blood flow regulation as measured by Transcranial Doppler and improved cardiovascular function as measured by changes in heart rate variability and maximal oxygen consumption (VO₂ max) compared to the control condition.

Sub-aim 3 Warfighter Performance: To determine if SAET participants will have improved locomotion and a higher level of occupational performance compared to the control condition.

Sub-Hypothesis 3: SAET participants will have improved locomotion and physical performance (based on the Marine Corps Combat Fitness Test (CFT)) and higher ratings of occupational performance (based on supervisor ratings on the Checklist of Military Activities of Daily Living (M-ADL)) after completion of treatment and 3 months post-treatment compared to the control condition.

Surveys, Questionnaires, and Other Data Collection Instruments

Test	Purpose	Description
Neurobehavioral Symptom Inventory (NSI)	Primary Aim	The NSI is a 22 item self-report questionnaire that assesses PCS (Cicerone & Kalmar, 1995). The questionnaire is a preferred measure by the DoD and Veteran Affairs. It is well-validated in research studies on TBI and PTSD in military populations, it has known reliability and validity, as well as guidelines for assessment of change (Belanger et al., 2016; Soble et al., 2014). Test-retest reliability values ranged from .78 to .94 for the total score and from .52 to .91 for subscales (Silva, 2021).
Symbol Digit Modalities Test (SDMT)	Secondary Aim 1	Utilized to measure divided attention, visual searching and tracing, and motor speed (Smith, 2007). The test is comprised of a coding key made up of nine abstract symbols. Each symbol has a corresponding number. The test-taker is asked to visually search the key and record the number that matches each symbol as quickly as they can. The test-retest reliability is 0.80. The SDMT has good validity with other tests of attention ($r = .62-.78$). The test will be purchased from a commercial vendor, which will allow authorized use of this measure.
Paced Auditory Serial Addition Test (PASAT)	Secondary Aim 1	A serial addition task used to assess attentional processing by examining the role of immediate memory and attention (Gronwall, 1977). During administration, a series of single digit numbers are presented where the two most recent digits must be summed. The PASAT has well-studied psychometric properties with good test-test reliability and validity (Strauss et al., 2006).
Hopkins Verbal Learning Test- Revised (HVLT-R)	Secondary Aim 1	Used to assess verbal learning and memory (Brandt et al., 1998). It is a brief test with six alternate forms that can be easily administered in patients with varying cognitive disorders. The test consists of three learning trials with 12 nouns (targets) and includes a 25-minute delayed free recall trial. This measure will be purchased from a commercial vendor which will provide permission for use in the study.
Delis-Kaplan Executive Function System Trail Making (DKEFS TM)	Secondary Aim 1	The DKEFS TM is a paper-and-pencil test consisting of five trials assessing mental flexibility and processing speed (Delis et al, 2001). It is a measure of psychomotor speed, visual search abilities, working memory, and cognitive flexibility. The score on each part of the TMT is determined by the time required to complete each trial. The test has been shown to have good reliability and

		validity when assessing acquired brain injury (Delis et al., 2001).
Delis-Kaplan Executive Function System Color Word (DKEFS CW)	Secondary Aim 1	The DKEFS CW is a measure of inhibition and top-down brain control (Delis et al., 2001). The test has several conditions which require the participant to read words quickly fluidly, name colors, inhibit over-learned responses, and switch between competing tasks. This study will focus on four (i.e., color naming, word reading, inhibition, inhibition/switching). The DKEFS CW task is widely utilized with good psychometric properties and validity for the assessment of individuals with TBI (Delis et al., 2001).
Combat Exposure Scale (CES)	Secondary Aim 1	The Combat Exposure Scale is a 7-item measure used to assess the participants' exposure to combat stress such as enemy fire and in-theater life and death situations (Keane et al., 1989). The 5-point scale for each item is weighted according to severity of exposure. The CES has a coefficient alpha of .85 and a 1-week test re-test of $r = .97$, $p < .0001$.
Post-Traumatic Stress Disorder Checklist (PCL-M)	Secondary Aim 1	The PCL-M is a self-report questionnaire which includes 17 items that are designed to assess symptoms of PTSD (Weathers et al., 1991). The PCL-M is extensively used both in clinical practice and is frequently used in research investigating PTSD and MTBI in military populations (Gerwitz et al., 2010; Belanger et al., 2010). This questionnaire is in the public domain and can be used without copyright restriction. The PCL-M has excellent diagnostic specificity. A conservative cut-off of 45 will be used which is consistent with recommendations from the National Center for PTSD. Empirical evidence suggests that this cut-off is associated with 97% specificity in active duty military (Bliese et al., 2008). Guidelines for assessment of changes for service members with MTBI have been published as well (Belanger et al., 2016).
Patient Health Questionnaire (PHQ-8)	Secondary Aim 1	The PHQ-8 is a version of the PHQ-9 that omits the question about suicidality. The PHQ-9 is the depression module of the self-administered version of the PRIME-MD diagnostic instrument (PHQ; Kroenke, 2001). The PHQ-9 is an instrument whose items are based on the SDM-IV diagnostic criteria for depression. Each of the 9 items can be scored from 0 (not at all) to 3 (nearly every day). Its validity and reliability as a diagnostic measure as well as its utility in assessing depression severity and monitoring treatment response are well-established (Lowe et al., 2004). It also has demonstrated reliability and validity for diagnosing depression in patients with MTBI (Fann et al., 2005). This questionnaire is in the public domain and can be used without copyright restriction.
Patients' Global Impression of Change (PGIC) Scale	Secondary Aim 1	The self-report measure Patient Global Impression of Change (PGIC) reflects a patient's belief about the efficacy of treatment. Although widely used in chronic pain clinical

		trials, PGIC's validity has not been formally assessed. PGIC is a 7 point scale depicting a patient's rating of overall improvement.
Pittsburgh Sleep Quality Inventory (PSQI)	Secondary Aim 1	A self-rated questionnaire which assesses sleep quality and disturbances over a 1- month time interval. It measures subjective sleep quality, sleep latency, sleep duration, habitual sleep efficiency, sleep disturbances, use of sleep medication, and daytime dysfunction over the last month. The PSQI takes approximately 3 minutes to administer.
Key Behaviors Change Inventory (KBCI)	Secondary Aim 1	The KBCI is a 64-item questionnaire that assesses behavioral areas such as lack of motivation, difficulties communicating, lack of insight into difficulties, and relationship problems (Kolitz et al., 2003). The instrument has good content and construct validity and an internal consistency reliability of 0.82-0.91.
Blast Exposure Threshold Study (BETS)	Secondary Aim 1	The BETS is a self-report survey that was designed to assess occupational blast exposure from military personnel. The standardized measurement tool efficiently records and calculates cumulative, life-long exposure to potential sources of blast overpressure. The BETS development was supported by the JPC-5 Exposure Standards Working Group and will be included in our study in order to better understand blast exposure history relative to outcome from CR in mTBI.
Rey-15	Secondary Aim 1	Rey-15 Item Test and Recognition The Rey-15 Item Test measures exaggeration or pretending to have memory problems. The test-taker is given a sheet of paper that has no markings. A card with 15 items is presented to the examinee. The test-taker is allowed to look at the card for a total of 10 seconds. Following this time period, the examinee is asked to record as many items from the card onto the paper as he or she can. Test-retest reliability is not available for the Rey-15. Inter-rater reliability has found 95% agreement for items correct, and 97% agreement for rows correct. Validity with other effort measures (e.g. Test of Memory Malingering (TOMM), Dot Counting Test (DCT)) ranges from $r = .19-.78$.
Test of Premorbid Functioning (TOPF)	Secondary Aim 1	The TOPF is used to determine premorbid intellectual functioning in adults (NCS Pearson Corporation, 2009). When administering the TOPF, the participant is given a list of 50 words and asked to pronounce the words as best they can in consecutive order even if they think the pronunciation is incorrect. Only when the participant has incorrectly pronounced 12 words in a row is the test stopped. The TOPF allows for a direct comparison to the WMS and the WAIS due to its development and standardization occurring at the same time. The internal consistency for the TOPF is excellent, ranging from .90-.97, and high test-retest reliability, .90-.94 is displayed. The TOPF also positively correlates with the Full Scale IQ (FSIQ), .63-.80, and the

		VCI, .61-.80 [NCS Pearson Corporation, 2009]. The TOPF takes approximately 5 minutes to administer.
Transcranial Doppler	Secondary Aim 2	Transcranial Doppler ultrasound is a non-invasive, painless procedure which is utilized to detect medical issues affecting blood flow/circulation in and around the brain using sound waves (Purkayastha & Sorond, 2012). Specifically, they are used to evaluate whether the small vessels regulating brain blood flow are working properly. This procedure is rapid and safe. It has been shown to be sensitive to changes in cerebral blood flow related to ANS dysfunction following TBI (Clausen et al., 2016)
Maximal Aerobic Capacity (VO ₂ max)	Secondary Aim 2	VO ₂ max is a numeric representation of the maximum amount of oxygen that is usable by the body during intense exercise, reflecting the aerobic or cardiovascular fitness level of an individual. The Korr Cardio Coach Plus will be used to capture VO ₂ . The Korr Cardio Coach Plus has been shown to accurately measure submaximal and maximal VO ₂ (Dielic-Conwright, Jensky, Battaglia, McCauley, & Schroeder, 2009).
Balance	Secondary Aim 2	The Bertec Balance Master Smart Balance Manager will be used to asses balance dysfunction pre and post intervention. Patients are secured to the balance platforms via straps with carabiners which attach to a vest being worn by the patient. Once the patient is properly secured, the balance test can begin by selecting the appropriate assessment such as motor control, mobility, weight shifting, etc. The Bertec uses an encircled dome surrounding the balance platform, which projects a moving background giving patients the sensation that they are moving using virtual reality technology (Quintana et al., 2021).
Marine Corps Combat Fitness Test (CFT)	Secondary Aim 3	The CFT is composed of an 880 yard run, max repetitions of an overhead lift of a 30-pound ammunition can, and performance during an under-fire simulated event and completed by all Marines regardless of gender or age. A mock CFT will be proctored by study personnel at baseline, post-treatment, and three months post-treatment.
Military Activities of Daily Living (M-ADL)	Secondary Aim 3	The M-ADL is an evaluation survey which includes 18 items designed to assess performance of SMs by their direct supervisors
Ohio State University Traumatic Brain Injury Identification Method (OSU-TBI ID)		The OSU-TBI ID is a standardized procedure for eliciting a person's lifetime history of TBI via a 3-5 minute structured interview. The validity of the OSU TBI-ID is not based on a perfect accounting of a person's lifetime history of TBI, it is a means to estimate the likelihood that consequences have resulted from one's lifetime exposure

At any point in the study, will you request, use, or access health information in any form, including verbal, hard copy and electronic?

The Military Health System (MHS) is defined as all DoD health plans and DoD health care providers that are organized under the management authority of, or in the case of covered individual providers, assigned to or employed by, the Defense Health Agency (DHA), the Army, the Navy, or the Air Force

MHS workforce members are employees, volunteers, trainees, and other persons whose conduct, in the performance of work for the MHS, is under the direct control of the MHS, whether or not they are paid by the MHS.

MHS business associates are persons or entities that provide a service to the MHS and require protected health information (PHI) to provide the service.

Are you an MHS workforce member? Yes

Are you an MHS business associate? No

Have you consulted with an MHS data expert to determine the data elements required for your study?

Consulting with a data expert often saves time later in the compliance process because the data expert can advise on the data available in the numerous MHS information systems, the quality of that data and the methods for encrypting and collapsing data. To schedule a consult with an MHS data expert, send an email to: ([contact])

Yes, then complete the questions below according to the data consult

No, then complete the questions below according to the best of your knowledge

Indicate how you will request data from the MHS. Select all that apply.

Talking with MHS health care providers or MHS health plans about specific research participants

Obtaining MHS hard copy records specific to research participants

Obtaining data from an MHS information system(s) YES

If you are obtaining data from an MHS information system(s), indicate whether you plan to receive a data extract or whether you plan to access an MHS information system directly to create a data set.

A data extract is when the MHS or a contractor provides the data set directly to the researcher. When receiving a data set through data extract, the researcher may indicate whether the data elements should be provided as is, encrypted or collapsed. In contrast to a data extract, access to an information system means that the researcher may directly access an MHS information system and create a data set for the research study.

Data Extract

Access YES

Do you intend to request de-identified data from the MHS in your research study?

There are different two methods for de-identifying data pursuant to HIPAA:

- 1) Safe Harbor Method: Removing all of the identifiers listed in Table 1 below, provided that the researcher does not have actual knowledge that the remaining data can be used alone or in combination with other information to identify the individual who is the subject of the information
- 2) Statistical Method: An expert, with appropriate knowledge of and experience with generally accepted statistical and scientific principles and methods for rendering information not individually identifiable, determines that the data is not individually identifiable

Yes

No

Indicate the MHS information system(s) from which you will seek to obtain data

If you do not know which system(s) contains the data elements you need, refer to the Guide for DoD Researchers on Using MHS Data or request guidance from an MHS data expert at: [contact].

Below is a list of commonly used MHS systems. If the system from which you seek to obtain data is not listed below, list the name of the system in the “Other MHS Systems” category below:

PHI Systems:

PII-only Systems

De-identified Data & Other Systems – MHS Genesis

Do you intend to merge or otherwise associate the requested data with data from any sources outside of the MHS, including other DoD systems that are not part of the MHS?

Yes, will merge data

No, will not merge data

Indicate the data elements about research participants or relatives, employers, or household members of the research participants that you will request from MHS hard copies or from MHS information systems.

List of requested variables from medical records

Category	Variables
Demographics	Age Sex Race/Ethnicity Highest level of schooling completed Marital status
Military information	MOS Rank Deployment number Unit Branch of service
Medical encounters	Encounters specific to concussion Encounters non-specific to concussion Specialties of providers seen

Follow-up information	
Mental health diagnosis	Depression Anxiety PTSD Current substance abuse disorder Current, active suicidal or homicidal ideation Other mental health conditions
Medications	List of any medications
Comorbidities	History of neurological disease other than concussion (e.g., multiple sclerosis, cerebral vascular accident, brain tumor, neurodegenerative disease, or neuro-motor disorder)
Cognitive assessments prior to study initiation	Determination of impaired decision-making capacity
